3.1.1 Study Treatment

Patients in both treatment arms will receive up to 1 year of treatment with either atezolizumab or placebo. Treatment will be administered intravenously on Day 1 of each 21-day cycle. Treatment will be discontinued in the event of disease recurrence, unacceptable toxicity, consent withdrawal, or study termination by the Sponsor.

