4.5.5 Surveillance for Renal Cell Carcinoma Recurrence

Patients will be assessed for tumor recurrence every 3 months (± 2 weeks) for Years 1–3 and every 6 months (± 4 weeks) thereafter until occurrence of an IRF-assessed DFS event, death, loss to follow-up, withdrawal of consent, or study termination, whichever occurs first, regardless of length of treatment/observation (See [Appendix 9](#) for details regarding assessment of RCC recurrence). Tumor recurrence will be assessed by an independent central radiologic review and investigator assessment.

Surveillance for tumor recurrence will include clinical history, physical examination, (as clinically indicated), laboratory evaluation, (as clinically indicated or per local surveillance guideline for RCC recurrence), and imaging studies of the chest, abdomen, and pelvis.

All eligible patients will undergo a contrast-enhanced CT of the chest, abdomen, and pelvis at screening no more than 4 weeks prior to randomization. MRI of the abdomen and pelvis with a non-contrast CT scan of the chest may be used in patients for whom CT scans with contrast are contraindicated (i.e., patients with contrast allergy or impaired renal clearance). Eligibility will be confirmed by an independent central radiologic review of imaging data, supported/confirmed by biopsy results (from biopsies performed before or during the screening period), as well as any historical scans which may support the interpretation of benign radiographic objects.

If a CT scan for tumor assessment is performed in a positron emission tomography PET/CT scanner, the CT acquisition must be consistent with the standards for a full-contrast diagnostic CT scan.

Surveillance imaging studies should use the same imaging modality that was used at screening and must be performed at the timepoints specified in [Appendix 1](#), regardless of drug delays or interruptions. Other examinations such as bone scan should be performed as clinically indicated.

If recurrent disease or occurrence of a new primary tumor is suspected on clinical grounds, imaging studies must be performed expeditiously, even if not mandated in the Schedule of Assessments.

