4.5.8 Patient-Reported Outcomes

Patient-reported outcome (PRO) data will be collected to document patients' perspective regarding the treatment burden. The questionnaires will be translated as required in the local language.

To ensure instrument validity and that data standards meet health authority requirements, questionnaires scheduled for administration during a clinic visit will be completed in their entirety by the patient before the patient receives any information on disease status that might bias the patient's answers and prior to the performance of non-PRO assessments and the administration of study treatment. Study site staff will ensure that PRO questionnaires are provided to the patients for completion per the Schedule of Assessments (see [Appendix 1](#)), and before the patients complete the visit the site staff will confirm completion or alternatively document any reasons for not completing the questionnaires.

All patients should complete the FKSI-19 and the EQ-5D-5L questionnaires at baseline (Cycle 1, Day 1) and at the beginning of each odd-numbered cycle (i.e., Cycles 3, 5, 7, 9, 11, 13, and 15).

Patients who discontinue study treatment will continue to complete the questionnaires at the end of treatment visit, the post-treatment visit, any visit for assessment of RCC recurrence, and at two timepoints after disease recurrence during survival follow-up.

Patients will complete PRO questionnaires at the clinic during the visits; data will be entered in the eCRF. If patients are no longer receiving treatment, it is expected that patients will not come to the clinic and therefore, the questionnaires will be administered

by the site staff over the phone and recorded in the eCRF. The instructions for completing the PRO questionnaires will be provided by site staff. The data will be subsequently captured electronically and included in the study centralized database maintained by the Sponsor. The data will be available for access by appropriate study personnel.

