5.1.2 Management of Patients Who Experience Specific Adverse Events

There will be no dose modifications for atezolizumab/placebo in this study.

Study drug (atezolizumab or placebo) may be temporarily suspended in patients who experience toxicity considered to be related to study treatment. If study drug is withheld for >42 days from the last dose, the patient will be discontinued from study drug. If the investigator believes the patient is likely to derive clinical benefit and the Medical Monitor is in agreement, study drug can be resumed after being withheld for >42 days. If a patient must be tapered off steroids used to treat adverse events, the study drug may

be withheld for additional time beyond 42 days from the last dose until steroids are discontinued or reduced to prednisone dose (or dose equivalent) ≤ 10 mg/day. The investigator and the Medical Monitor will determine the acceptable length of treatment interruption.

Dose interruptions for reasons other than toxicity (e.g., surgical procedures) may be allowed *per investigator discretion*. The investigator *may consult* the Medical Monitor *to* determine the acceptable length of treatment interruption.

Guidelines for the management of patients who experience specific adverse events associated with atezolizumab are provided in [Appendix 11](#).

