- ^t Baseline sample to be collected on Cycle 1, Day 1 prior to the first dose of study treatment. For patients who show evidence of immune-mediated toxicity, additional samples will be collected, and all samples will be analyzed centrally. Includes CRP, anti-nuclear antibody, anti-double stranded DNA, circulating anti-neutrophil cytoplasmic antibody, and perinuclear anti neutrophil cytoplasmic antibody.
- ^u Whole blood for DNA isolation will be collected from patients who have consented to optional RBR sampling at Cycle 1, Day 1. If, however, the RBR genetic blood sample is not collected during the scheduled visit, it may be collected as soon as possible (after randomization) during the conduct of the clinical study.
- ^v Patients will receive their first dose of study drug the day of randomization, if possible. If this is not possible, the first dose should occur no later than 5 days after randomization. The initial dose of treatment will be delivered over 60 (\pm 15) minutes. If the first infusion is well tolerated, all subsequent infusions may be delivered over 30 (\pm 10) minutes. Study treatment may be continued for a maximum of 16 cycles (or 12 months, whichever occurs first) in the absence of disease recurrence, unacceptable toxicity, withdrawal of consent, or study termination by the Sponsor.

Appendix 1

Schedule of Assessments (cont.)

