Appendix 1 Schedule of Assessments (cont.)

- ^{bb} Survival follow-up information will be collected via telephone calls, patient medical records, and/or clinic visits approximately every 3 months (± 7 days) until death, loss to follow-up, consent withdrawal, or study termination by the Sponsor. All patients (irrespective of which arm they are randomized to) will be followed for survival and new anti-cancer therapy information (including targeted therapies and immunotherapies) and subsequent progressions, unless the patient requests to be withdrawn from follow-up; this request must be documented in the source documents and signed by the investigator. If a patient withdraws from *the* study, study staff may use a public information source (e.g., county records) to obtain information about survival status.
- ^{cc} The PRO questionnaires (FKSI-19 and EQ-5D-5L) will be completed by the patients at the investigational site while patients are receiving study treatments. All PRO questionnaires completed at the clinic are required to be completed prior to the exchange of meaningful information (e.g., lab results), prior to administration of study treatment and/or prior to any other study assessment(s) that could bias patients' responses to ensure that the validity of the instruments is not compromised and to ensure that data quality meets regulatory requirements. Study personnel should review all questionnaires for completeness before the patient leaves the investigational site, and the hard copy originals of the questionnaires must be maintained as part of the patient's medical record when relevant at the site for source data verification. Study personnel will record patient responses on a paper copy as a record of source documentation.
- ^{dd} Odd-numbered cycles only (i.e., Cycles 1, 3, 5, 7, 9, 11, 13, and 15).
- ^{ee} After discontinuation of the study treatment, the PRO questionnaires will be administered by trained site staff over the phone or at the site at end of treatment visit, the post-treatment visit, any visit for assessment of RCC recurrence, and at two timepoints after disease recurrence during survival follow-up.

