Dyspnea, cough, fatigue, hypoxia, pneumonitis, and pulmonary infiltrates have been associated with the administration of atezolizumab. Patients will be assessed for pulmonary signs and symptoms throughout the study and will also have computed tomography (CT) scans of the chest performed at every tumor assessment.

All pulmonary events should be thoroughly evaluated for other commonly reported etiologies such as pneumonia or other infection, lymphangitic carcinomatosis, pulmonary embolism, heart failure, chronic obstructive pulmonary disease, or pulmonary hypertension. Management guidelines for pulmonary events are provided in [Table 1](#).

Appendix 11

Risks Associated with Atezolizumab and Guidelines for Management of Adverse Events Associated with Atezolizumab (cont.)

Table 1 Management Guidelines for Pulmonary Events, Including Pneumonitis

Event	Management
Pulmonary event, Grade 1	
 • Continue atezolizumab and monitor closely. • Re-evaluate on serial imaging. • Consider patient referral to pulmonary specialist. • For Grade 1 pneumonitis, consider withholding atezolizumab.
Pulmonary event, Grade 2	
 • Withhold atezolizumab for up to 12 weeks after event onset.^a • Refer patient to pulmonary and infectious disease specialists and consider bronchoscopy or BAL. • Initiate treatment with 1–2 mg/kg/day oral prednisone or equivalent. • If event resolves to Grade 1 or better, resume atezolizumab.^b • If event does not resolve to Grade 1 or better while withholding atezolizumab, permanently discontinue atezolizumab and contact Medical Monitor.^c • For recurrent events or events with no improvement after 48–72 hours of corticosteroids, treat as a Grade 3 or 4 event.
Pulmonary event, Grade 3 or 4	
 • Permanently discontinue atezolizumab and contact Medical Monitor.^c • Bronchoscopy or BAL is recommended. • Initiate treatment with corticosteroids equivalent to 1–2 mg/kg/day IV methylprednisolone. • If event does not improve within 48 hours after initiating corticosteroids, consider adding an immunosuppressive agent. • If event resolves to Grade 1 or better, taper corticosteroids over ≥ 1 month.

BAL=bronchoscopic alveolar lavage.

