Time to confirmed deterioration (TTCD) analyses will be performed for each FKSI-19 subscale and Total scale in the ITT population. TTCD is defined as the time from the date of randomization to the date of a clinically meaningful score change from baseline that is held for at least two consecutive timepoints, or followed by death within 6 weeks from the last PRO assessment. Patients who do not experience a confirmed deterioration event at the time of clinical data cutoff will be censored at the last timepoint when they completed an assessment. Patients with no baseline or no post-baseline assessment will be censored at the randomization date. TTCD using the FKSI-19 scale will be analyzed similarly to the analysis of investigator-assessed DFS.

A clinically meaningful score change is defined as a 3-point or more score decrease on the FKSI-19 Total scale and DRS subscale (Cella et al. 2007, Yost and Eton 2005); a 4 point or more score decrease on the DRS-P subscale; and a 1-point or more score decrease on the DRS-E, TSE, and FWB subscales (Cella et al. 2018, Yost and Eton 2005).

Overall AE burden, as measured by the FKSI-19 GP5 item, will be summarized descriptively (numbers and proportions of responses) at each assessment timepoint in the safety-evaluable population. The distribution of responses and/or change from baseline will be illustrated by stacked bar charts for each arm.

To assess the consistency of the FKSI-19 results, the TTCD analysis (as defined above) will be performed on the subgroups defined by demographic and baseline characteristics. The outputs will include unstratified HRs estimated from the Cox proportional hazards model with associated 95% confidence intervals and, Kaplan-Meier estimates of the median will be produced separately for each level of the subgroup.

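### On-treatment questionnaires follow dosing cycles with no calendar anchor, so a toxicity hold probably opens a gap in the patient-reported tolerability data

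*Protocol*

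**What the plan says.** **When forms are due.** Protocol Section 4.5.8 schedules FKSI-19 and EQ-5D-5L "at baseline (Cycle 1, Day 1) and at the beginning of each odd-numbered cycle". Appendix 1, footnote dd, repeats this: "Odd-numbered cycles only (i.e., Cycles 1, 3, 5, 7, 9, 11, 13, and 15". Section 3.1.1 ties cycles to dosing: "Treatment will be administered intravenously on Day 1 of each 21-day cycle". A second schedule (end of treatment, post-treatment visit, recurrence-assessment visits, two timepoints after recurrence) is written for patients who have discontinued treatment (Section 4.5.8; Appendix 1, footnote ee).

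**Holds.** Section 5.1.2 says study drug "may be temporarily suspended in patients who experience toxicity considered to be related to study treatment". It sets discontinuation once the drug has been withheld more than 42 days from the last dose, with exceptions. Appendix 11 allows most holds to run up to 12 weeks from event onset, also extendable. Its usual condition for restarting, as in Table 1, is "If event resolves to Grade 1 or better, resume atezolizumab", preceded by a taper of at least a month if corticosteroids were started.

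**Treatment cap.** Appendix 1, footnote v: "Study treatment may be continued for a maximum of 16 cycles (or 12 months, whichever occurs first".

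**Imaging, for contrast.** Section 4.5.5 keeps surveillance scans at their timepoints "regardless of drug delays or interruptions". The questionnaire section has no such clause.

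**Analysis.** SAP Section 5.7.5.1 counts confirmed deterioration when a meaningful score change occurs "that is held for at least two consecutive timepoints", or is followed by death within 6 weeks of the last form. A meaningful drop is 3 points on Total and DRS, 4 on DRS-P, and 1 on DRS-E, TSE and FWB. Missing data are not imputed.

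**The concern.** A patient on a temporary hold falls between the two questionnaire schedules. No odd-numbered cycle is starting, and treatment has not been discontinued. For most held events the drug restarts only after recovery to Grade 1 or better, so the next on-treatment form tends to describe a recovered patient. Whether a form is scheduled then depends on toxicity itself, and no analysis rule can recover a form that was never due.

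FKSI-19 is the only endpoint listed for the objective on patients' view of tolerability and quality of life. The GP5 summary of side-effect burden and the EQ-5D utilities rest on the same visits. The SAP's compliance rate divides by the patients expected to complete a form, so a postponed form may not even show as missing.

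**Working it through.** The documents give no figure for this point, so the check is schedule arithmetic.

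**Assumption.** A cycle starts when its dose is given, so a hold moves all later cycles. The documents do not say this. The indirect support is the treatment cap: 16 × 21 = 336 days, which leaves 365 − 336 = 29 days before 12 months. The 12-month limit can bind only if cycles run late.

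**Gap between consecutive on-treatment forms.** Let r be the days from the last dose to resumption.
- Last dose in an odd cycle: the drug resumes with an even cycle after r days, and the next odd cycle is 21 days later. Gap = r + 21.
- Last dose in an even cycle: the previous form was 21 days before that dose, and the drug resumes with an odd cycle. Gap = 21 + r.

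The two cases agree.

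| Situation | r (days) | Gap (days) |
|---|---|---|
| No hold | 21 | 42 |
| Hold to 42 days from last dose (Section 5.1.2) | 42 | 63 |
| Hold to 12 weeks from onset, onset 0 days after last dose (Appendix 11) | 84 | 105 |
| Same, onset 21 days after last dose | 21 + 84 = 105 | 126 |

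Extensions for steroid tapering would widen these gaps.

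**What a calendar would add.** With forms every 42 days, an 84-day hold contains two of them wherever it starts (84 / 42 = 2). The 21 extra days under the 42-day limit contain none or one.

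**Why a bias figure cannot be given.** For an episode of L weeks between 6 and 12, a 6-weekly calendar places two forms inside it with probability (L − 6)/6.
- If symptoms last 6 to 12 weeks, uniformly (assumed), the average is 50%.
- If a taper of about a month follows recovery, so that symptoms fill only 2 to 8 of those weeks (also assumed), only L from 6 to 8 contributes: (1/6) × (1/6) × (2²/2) = 2/36, about 6%.

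The documents give neither symptom duration nor the frequency of holds. The nearest figures are in Protocol Section 1.3.2.1: in the Phase Ia renal cohort, adverse events of special interest were Grade 2 in 11.4% and Grade 3 in 4.3% of patients, 15.7% together. That population was metastatic, and not every such event would lead to a hold.

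**The case against.** A reader might infer that a held episode can never count as confirmed deterioration. The documents do not support that. The form is completed before other assessments and before dosing (Section 4.5.8), and the decision to dose is taken at that visit (Section 4.5), so a hold decided at an odd-cycle visit already has one form. The next form after the hold is the consecutive timepoint, wherever it falls. Grade 1 is not the baseline score, and a residual 1-point drop on TSE or FWB is enough to confirm.

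Nor is every return to dosing tied to Grade 1. Symptomatic thyroid events and Grade 3 or 4 hyperglycemia have other conditions in Appendix 11.

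A reader might also infer that measurement stops during the worst toxicity. Much of it leads elsewhere: Grade 3 or 4 pulmonary, hepatic, ocular, renal and neuropathy events, Grade 4 colitis and Grade 2 to 4 myocarditis call for permanent discontinuation. So do most holds that do not resolve. Those patients move to the off-treatment schedule and keep reporting. Some held events are laboratory findings, such as amylase or lipase elevation, that need not change a questionnaire score.

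The cycle-shift premise is also only an inference. Appendix 1 allows ±3 days per visit from Cycle 2. If each of 15 intervals slipped by 3 days, 16 cycles would take 336 + 45 = 381 days with no toxicity hold, so the 12-month limit has another possible reason. If a withheld dose used up its cycle number and visits kept to 21 days, the gap would not arise.

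All of this limits the claim. None of it schedules a form during a hold for a patient who later resumes. Held patients still attend 3-monthly imaging, but the questionnaires at those visits are written for patients off treatment.

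**Conclusion.** The schedule has no calendar anchor and no provision for a hold. On the inferred reading that a hold delays the cycle count, the gap between forms rises from 42 days to 63 days under Section 5.1.2, or to 105 to 126 days under Appendix 11. The two limits differ in length and starting point, and the passages must be reconciled.

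Transient side-effect episodes are therefore under-recorded in FKSI-19, GP5 and EQ-5D-5L, and are less likely to be confirmed as deterioration. If holds are commoner on atezolizumab, which is an assumption, the bias is toward no difference in tolerability. Its size cannot be fixed from the documents.

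The effect is confined to exploratory and health-economic endpoints. The DFS and OS tests are untouched, and adverse events, including those leading to interruption, are summarized separately. This is a cheap improvement to a secondary part of the plan, not a flaw in its main inference.

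**What to change.** In Section 4.5.8 and Appendix 1, footnote dd, schedule FKSI-19 and EQ-5D-5L every 6 weeks from Cycle 1 Day 1, at Weeks 6, 12, 18, 24, 30, 36 and 42. Add the clause that Section 4.5.5 already uses for imaging, so that the dates hold through dose delays. The forms are completed at whatever visit falls in the window, or by phone if none does. For a patient dosed on time these weeks coincide with Cycles 3 to 15, so nothing changes. The text should also say whether a withheld dose uses up a cycle number.

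The cost is a wording change and one or two extra sessions of about 10 minutes per held patient (about 5 minutes per questionnaire), some by phone rather than in clinic; phone administration is already in the protocol for patients off treatment. A delayed patient still being dosed after Week 42 would next report at the end-of-treatment visit.

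Where dosing is already complete, the clinical study report can give the frequency of holds and the gaps between forms by arm, and state the limitation.

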4.5.8.1 EuroQol 5–Dimension 5–Level Questionnaire

The EQ–5D–5L is generic preference-based health utility questionnaire that provides a single index value for health status (see [Appendix 6](#)). The EQ–5D–5L comprises questions about mobility, self-care, usual activities, pain/discomfort, and anxiety/depression that are used to build a composite of the patient’s health status. In addition, the EQ-5D-5L includes a visual analog scale for the patient to rate his or her current health status. The EQ-5D-5L will be utilized in this study for the purpose of deriving utilities for economic modeling, not to document treatment benefit. The EQ-5D-5L questionnaire takes 5 minutes or less to complete.

4.5.8.2 National Comprehensive Cancer Network Functional Assessment of Cancer Therapy Kidney Symptom Index (FKSI-19)

The FKSI–19 is a 19-item tool designed to assess the most important symptoms and concerns related to evaluating treatment effectiveness in advanced kidney cancer (Butt et al. 2013). The FKSI–19 includes symptoms commonly experienced with cancer or with immunotherapy including, fatigue, shortness of breath, fever, and bone pain. In addition, the questionnaire includes items that capture patients’ difficulty with the side effects of treatment, the ability to work, the ability to enjoy life, and contentment. Each item is scored on a five-point scale (0–4) with each level corresponding to: 0=“Not at all,” 1=“A little bit,” 2=“Somewhat,” 3=“Quite a bit,” and 4=“Very much.” The questionnaire takes approximately 5 minutes to complete.

4.5.9 Optional Samples for Research Biosample Repository

4.5.9.1 Overview of the Research Biosample Repository

The RBR is a centrally administered group of facilities used for the long–term storage of human biologic specimens, including body fluids, solid tissues, and derivatives thereof (e.g., DNA, RNA, proteins, peptides). The collection, storage, and analysis of RBR specimens will facilitate the rational design of new pharmaceutical agents and the development of diagnostic tests, which may allow for individualized drug therapy for patients in the future.

Specimens for the RBR will be collected from patients who give specific consent to participate in this optional research. RBR specimens will be used to achieve the following objectives:

- To study the association of biomarkers with efficacy, adverse events, or disease progression
- To increase knowledge and understanding of disease biology

- To study drug response, including drug effects and the processes of drug absorption and disposition
- To develop biomarker or diagnostic assays and establish the performance characteristics of these assays

